### 3. STUDY DESIGN AND SCHEDULE OF EVENTS

This is a randomized, open-label, controlled phase 2 trial designed to evaluate the safety and tolerability and explore the efficacy of CAP-1002 administered by multi-vessel intracoronary infusion in subjects with cardiomyopathy secondary to DMD. Approximately 24, and not more than 30, subjects will be randomized 1:1 to receive CAP-1002 or usual care. Subjects randomized to receive usual care will continue to be cared for and treated on an ongoing basis in whatever manner the investigator deems most appropriate for the subject. The first 6 subjects enrolled (Group 1) will be older than 18 years of age. Enrollment of the remaining subjects (Group 2) will begin at least two weeks after the final infusion occurs in Group 1 to allow a review of Group 1 safety data through 72 hours post infusion. Subjects in Group 2 will be at least 12 years of age.

CCI

Anatomically  
one of the three coronary arteries infused must supply more than 30% of the LV myocardium.

Subjects will undergo protocol assessments through 12 months post infusion or reference date. Reviews by a Data Safety Monitoring Board (DSMB) will be done after Group 1 completes 72 hours of follow-up and throughout the trial per charter but at least semi-annually. The DSMB will review both safety and efficacy data after all subjects complete 6 months of follow-up or withdraw from the study. In addition, there will be one administrative interim efficacy analysis after Month 6 MRI measurements are available for at least 14 subjects. Subjects will be followed annually for 5 years post infusion or reference date. The Schedule of Events is shown in [Appendix A](#). A schematic of the study design is as follows:

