## 4. SAMPLE SIZE

The sample size of approximately 12 subjects per treatment group is adequate to assess safety and tolerability and to explore efficacy.

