### 7.3 Data Analysis

- The anchor date used for summaries and analyses will depend on the analysis population, as follows:
  - ITT population: randomization date
  - mITT population: IP administration or reference date

- Safety population: IP administration or reference date
- Per protocol population: IP administration or reference date
- Categorical variables will be summarized as frequencies and percentages in each category. Percentages will be reported to one decimal place. Unless otherwise noted in Sections 8-10, categorical variables will be analyzed using chi square tests of association or, if any contingency table cell has less than 5 subjects, Fisher's exact test.
- Continuous variables will be summarized by numbers of subjects, means, standard deviations, medians, and ranges. The number of decimal places for minimums and maximums will be the same as the original data. The number of decimal places for means, medians, and interquartile ranges will be the same as the original data plus one. The number of decimal places for measures of variance will be the same as the original data plus two. Unless otherwise noted in Sections 8-10, continuous variables will be analyzed using t-tests or, if appropriate, analysis of covariance with baseline as a covariate. Non-parametric tests and data transformations will be considered for variables with distributions that violate parametric assumptions.
- Data with qualifiers (e.g., “<”) will be listed with but summarized without the qualifier.
- P-values will be presented to two decimal places if  $> 0.01$ , to three places if  $< 0.01$  but  $> 0.001$ , and to four places if  $< 0.001$  but  $> 0.0001$ . P-values  $< 0.0001$  will be presented as “ $< 0.0001$ .”
- Statistical tests will be two-sided and tested at the 0.05 significance level unless otherwise noted in Sections 8-10.
- It is understood that statistical non-significance is not an indicator of equivalence.

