### 9.1 Adjudicated Clinical Events

Clinical events, described in [Section 2.3.1](#), will be adjudicated by an independent Clinical Events Committee (CEC) (see [Section 12](#)). Each event will be summarized as frequency and percentage of subjects who experienced the event. In addition, a composite event will be defined as new TIMI flow 0-2 or TMPG 0-2 (CAP-1002 subjects only), sudden death, or MACE during or following IP administration or reference time point. For the composite and its components, summaries will include exact 90% confidence intervals (CIs) for both treatment groups. For peri-procedural events other than TIMI flow 0-2 or TMPG 0-2, summaries will include a 90% CI for the difference in proportions between treatment groups, and the one-sided p-value from an exact binomial test of the difference between treatment groups. For all other clinical events, assessed over the length of the trial, event rates per 100 subject-years will be calculated and, if applicable, treatment groups will be compared using negative binomial regression with an offset for days of follow-up (log transformed). If the dispersion parameter is not significantly different from zero, Poisson regression will be used instead.

For the analysis of development of increased HLA antibodies to HLA antigens specific to the CAP-1002 donor, incidence of increased HLA antibody levels specific to the donor will be summarized and analyzed; for usual care subjects, a random donor will be selected from those that were matched to the subject during screening. Elevated levels of donor specific antibodies will also be summarized and analyzed by time point for all nominal time points at which samples were collected for DSA testing. Analyses will be performed using both 1000 and 5000 MFI as the threshold for defining increased HLA antibodies.

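### SAP 9.1 leaves the between-arm test of follow-up clinical events undefined when an arm has no events, and picks Poisson by a dispersion test with little power at about 12 per arm

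*SAP*

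**What the plan says.** Safety is the primary objective (SAP 2.1). For adjudicated clinical events, SAP 9.1 starts with a model-free summary: "Each event will be summarized as frequency and percentage of subjects who experienced the event". Peri-procedural events other than the TIMI/TMPG finding get an exact between-arm test, and the composite and its components get exact 90% intervals within each arm.

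For all other clinical events over the trial, "event rates per 100 subject-years will be calculated". Where applicable (a qualifier left undefined), the arms are compared by negative binomial regression with log follow-up time as offset. Then comes the switching rule: "If the dispersion parameter is not significantly different from zero, Poisson regression will be used instead".

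The section does not say whether the treatment effect or the dispersion is tested by a Wald, likelihood-ratio (LR), score or exact method. SAP 7.3 sets the level: "Statistical tests will be two-sided and tested at the 0.05 significance level unless otherwise noted in Sections 8-10". The same section makes Fisher's exact test the default for sparse categorical data, but again only where Sections 8-10 do not say otherwise, so 9.1 displaces it here. On size, SAP 4 says: "The sample size of approximately 12 subjects per treatment group is adequate to assess safety and tolerability and to explore efficacy". No event rate, dispersion or power is given for these events.

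**The concern.** Two features of the rule fit poorly with two arms of about 12.

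First, sparse events make an empty arm likely. The maximum-likelihood rate ratio is then zero or infinite, and the p-value depends on which test the analyst or the software default supplies. The case in which the choice matters most, events in one arm only, is the one for which 9.1 has no rule.

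Second, the switch to Poisson treats a non-significant dispersion parameter as evidence of no overdispersion. SAP 7.3 itself warns against reading non-significance as equivalence. If one subject can have several events, Poisson standard errors are too small.

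At stake is the error rate of a between-arm comparison on the primary objective. The trial is open-label, so a test chosen after the data are seen could not be shown to be independent of them.

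**Working it through.** There is no figure in the plan to reproduce.

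**Inputs from the documents.** About 12 subjects per arm (SAP 4), 1:1 allocation and 12 months of follow-up (SAP 3), so about 12 subject-years per arm; two-sided 0.05 (SAP 7.3).

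**Assumptions.** 5-15% of subjects per arm with an event, or 0.1-2 events per subject-year; negative binomial dispersion k from 0.5 to 4; equal follow-up.

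**Step 1: chance of an empty arm.** If a proportion p of subjects in each arm has an event, P(at least one arm empty) = 1 - [1 - (1-p)^12]^2.
- p = 5%: 0.95^12 = 0.540, giving 1 - 0.460^2 = 79%.
- p = 10%: 0.90^12 = 0.282, giving 1 - 0.718^2 = 49%.
- p = 15%: 0.85^12 = 0.142, giving 1 - 0.858^2 = 26%.

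**Step 2: p-values for m events against 0, 12 v 12, equal follow-up.** The LR statistic from the Poisson model is 2m ln 2 on 1 df. The exact conditional p is 2 x 0.5^m. Fisher assumes one event per subject; for m = 5 it is 2 x C(12,5)/C(24,5) = 2 x 792/42504 = 0.037.

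| Events | Wald | LR | Exact conditional | Fisher |
|---|---|---|---|---|
| 3 v 0 | about 1 | 0.041 | 0.25 | 0.22 |
| 4 v 0 | about 1 | 0.019 | 0.125 | 0.093 |
| 5 v 0 | about 1 | 0.008 | 0.0625 | 0.037 |
| 6 v 0 | about 1 | 0.004 | 0.031 | 0.014 |

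The Wald p stayed between 0.9997 and 1.0 from 1 v 0 up to 20 v 0. LR is not a safe default either: at 3 v 0 it is significant where the exact test gives 0.25.

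**Step 3: power of the dispersion test.** Simulation, 3000 trials per setting, LR test at 0.05 with the ordinary 1-df critical value. The boundary-corrected value of 2.706 gives somewhat more power.

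| Events per subject-year | k = 1 | k = 2 | k = 4 |
|---|---|---|---|
| 0.1 | 1% | 2% | 6% |
| 0.25 | 5% | 11% | 27% |
| 0.5 | 15% | 37% | 59% |
| 1.0 | 45% | 74% | 89% |
| 2.0 | 84% | 96% | 98% |

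A Wald test of k has essentially no power up to 0.5 per year (at most 0.6%).

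**Step 4: true-null rejection by the two-step rule (nominal 5%).**
- At 0.1-0.3 per year: about 0-2% with Wald treatment tests, about 8-14% with LR treatment tests.
- At 1-2 per year with overdispersion: about 7-11%.

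These departures have different sources. At sparse rates much comes from the treatment test itself: Wald fails with empty or near-empty arms, and LR is anti-conservative at small counts (Step 2). At higher rates the pre-test matters more. At 2.0 per year with k = 0 the rule rejected in 5.5% of trials. With k = 1 it rejected in 8.7%, and in the trials where the pre-test chose Poisson the rejection rate was 22.6%.

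**The case against.** A reader might infer that any arm with no events gives p near 1 however strong the signal. The documents do not support that: 9.1 specifies a model and never names the Wald test. With LR, 6 v 0 gives 0.004; with the exact conditional test, 0.031. What stands is that 9.1 does not decide between them.

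A reader might also infer that the dispersion test cannot detect overdispersion. It can at higher rates: 45-98% LR power at 1-2 events per subject-year with k of 1 or more. The problem is low power at sparse rates.

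The strongest counter-argument is that other planned outputs cover the same ground, and it largely stands:
- SAP 9.2 gives incidence p-values for treatment-emergent SAEs and deaths, where the Fisher default of 7.3 applies. Deaths and hospitalizations are SAEs under Protocol 7.13.8.1.
- For the composite and its components, the exact 90% limits are at most 22.1% for 0/12 and at least 24.5% for 6/12, which do not overlap.
- Counts, percentages and rates are reported for every event, and the DSMB reviews clinical events at least every 6 months (SAP 13.1, 14).

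So a strong one-sided excess would be seen. These outputs still do not supply a defined between-arm test for the adjudicated follow-up endpoints.

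It is also fair that an empty arm is not in itself a wrong conclusion. Fisher is non-significant at 3 v 0 and 4 v 0 as well. With 10% of subjects affected in both arms, 5 or more against 0 arises in only about 0.24% of trials (2 x 0.9^12 x P[Bin(12, 0.1) >= 5]). That figure is for no treatment difference; it does not describe a trial with real harm in one arm. Finally, there is no powered safety hypothesis, and nothing in the documents ties a decision to this p-value.

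**Conclusion.** The point holds in limited form. At about 12 per arm the rule in SAP 9.1 is undefined in a likely situation: an empty arm in 26-79% of trials if 5-15% of subjects per arm have an event. It does not keep its nominal 5% level: about 0-2% or 8-14% at 0.1-0.3 events per subject-year, depending on the unnamed test, and about 7-11% at 1-2 per year with overdispersion. For 5 v 0 the permitted p-values run from about 1 to 0.008.

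All event rates and dispersions are assumptions, and equal follow-up is assumed throughout. The empty-arm problem and the larger overdispersion problem belong to different rate ranges: with the same Poisson rate in both arms, an empty arm occurs in 51% of trials at 0.1 per year but only 0.5% at 0.5. They should not be added together.

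The defect lies in this between-arm test. It would be wrong to conclude that the safety analysis as a whole fails. The change is cheap and worth making before database lock, but the trial's safety reading does not hinge on it.

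**What to change.** In SAP 9.1, replace the negative binomial/Poisson comparison with the following.

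1. Primary between-arm comparison of each follow-up event: two-sided Fisher's exact test on subjects with at least one event, with an exact confidence interval for the difference in proportions (method and level stated). This also covers an arm with no events and extends the exact approach that 9.1 already uses for peri-procedural events.
2. For events that can recur, add a re-randomization test on subject-level counts per time at risk, with the reference distribution generated by the allocation procedure in SAP 5.
3. Delete the dispersion pre-test.
4. Keep any model-based rate ratio as descriptive, fitted only when both arms have events.

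Cost: SAP wording and a short program; no new data, visits or subjects. There would be no model-based rate ratio when an arm is empty. The Fisher test ignores repeat events and differences in follow-up time, which is why item 2 is added for recurrent events.

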### 9.2 Adverse Events

AEs reported from screening through EOS will be coded according to MedDRA® (Medical Dictionary for Regulatory Activities) version 19.0. Each reported AE will be mapped to a Preferred Term (PT) and a System Organ Class (SOC). A subset of AEs (indicated below) will also be adjudicated by the independent CEC.

A treatment-emergent AE (TEAE) will be defined as an AE that began or worsened during or after the IP administration procedure or on or after the reference time point. AEs with insufficient date or time information to determine whether or not they were treatment-emergent will be considered treatment-emergent and the ambiguity regarding start time/date for these AEs will be footnoted in summary tables.

All TEAEs will be listed as reported. A separate listing will be done for TEAEs as adjudicated by the CEC. In addition, separate listings will be done for deaths, non-treatment-emergent AEs and serious AEs (SAEs), treatment-emergent SAEs (adjudicated), TEAEs within 24 hours of IP administration (adjudicated if judged to be related to IP or IP administration procedure), and TEAEs that resulted in study discontinuation (excluding deaths); these listings will be “as adjudicated,” as applicable. Deaths will be listed by primary cause as adjudicated by the CEC.

Incidence and number of TEAEs will be summarized by SOC and PTs within SOCs, both overall and by relationship to IP, relationship to IP administration, and severity. Relationship status “possibly,” “probably,” or “definitely” will be considered related and will be adjudicated. Missing relationship will be considered related for subjects in the CAP-1002 group and missing severity will be considered severe; the lack of assigned relationships for these AEs will be footnoted in summary tables. Only the most related TEAE per subject for a given PT will be counted in summaries by relationship; similarly, only the most severe TEAE will be counted in summaries by severity. Separate summaries will be done for treatment-emergent SAEs, TEAEs within 24 hours of IP administration, treatment-emergent deaths, and TEAEs resulting in study discontinuation (excluding deaths). Each summary table will include a p-value for the comparison of incidence for each SOC and PT, as well as overall, between treatment groups, if applicable. Summary tables and analyses will be based on TEAEs as adjudicated by the CEC.

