## 12. CLINICAL EVENTS COMMITTEE

In order to apply some level of consistency and standardization, the following will be adjudicated by a CEC:

- Clinical event endpoints
- AEs occurring within 24 hours of IP administration or reference time point (peri-procedural AEs)
- AEs judged by the investigator as possibly, probably or definitely related to the IP or IP administration procedure (related AEs)
- Treatment-emergent SAEs

The CEC will follow consensus definitions of cardiovascular endpoint events. In the case where the protocol explicitly provides an endpoint definition, the CEC will adjudicate the clinical event according to the protocol definition and then, separately, according to the consensus definition. In the case where the protocol provides only a partial definition (e.g., “emergency room treatment for heart failure”) or is silent on the definition of the endpoint, the consensus definition, if it exists, will be used.

For safety endpoints, a hierarchy will be applied for a clinical event that could be adjudicated in multiple categories so that a clinical event is counted only once. The hierarchy, from highest severity to lowest, will be death > heart failure hospitalization > cardiovascular-related hospitalization.

For any AE submitted to the CEC, all of the above characteristics will be adjudicated. In addition, the CEC can combine AEs reported separately into a single AE, can change the event description (i.e., the term used to report the AE), and can change the status of the reported event to a non-AE.

Any adjudicated event not otherwise named in the consensus definitions, as well as changed event descriptions, will be MedDRA-coded.

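### SAP 9.2 takes between-arm TEAE tables from CEC-adjudicated events, but late non-serious, non-endpoint TEAEs in practice reach the CEC only in CAP-1002, so the two columns follow different rules

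*SAP*

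**What the plan says.** SAP 9.2 plans TEAE incidence and event numbers by system organ class (SOC) and preferred term (PT), "both overall and by relationship to IP, relationship to IP administration, and severity". Each summary table is to carry a "p-value for the comparison of incidence for each SOC and PT, as well as overall, between treatment groups, if applicable". The section opens its account of adjudication with "A subset of AEs (indicated below) will also be adjudicated by the independent CEC" and closes with "Summary tables and analyses will be based on TEAEs as adjudicated by the CEC". Events rated possibly, probably or definitely related "will be considered related and will be adjudicated".

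SAP 12 gives four routes to the CEC. Two do not depend on timing or relatedness: an event is referred if it is one of the clinical endpoints, or if it is serious and treatment-emergent. The third is a first-day route open to both arms, worded as "AEs occurring within 24 hours of IP administration or reference time point (peri-procedural AEs"). The fourth is a relatedness route, which turns on the site's own rating: "AEs judged by the investigator as possibly, probably or definitely related to the IP or IP administration procedure (related AEs").

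For any AE that it receives, the CEC may merge it with another, change its description, or reclassify it as not an AE. SAP Appendix B plans TEAE listings both as reported (16.2.7.2.1) and as adjudicated (16.2.7.2.2), but no TEAE table labelled as reported.

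**The concern.** Safety is the primary objective, and the TEAE tables are one of its main outputs. A between-arm table is fair only if an event has the same chance of being counted, renamed or removed in either arm. Here one class of event passes through a committee in one arm and, in practice, not in the other. A CEC deletion or merger may be quite correct, but a similar late non-serious report in usual care would not be reviewed. Section 9.2 also does not say how TEAEs that never went to the CEC enter tables described as adjudicated, so a programmer could build the tables in two ways that err in opposite directions.

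**Working it through.** The plan has no figure to reproduce: SAP 4 gives about 12 subjects per group, with no TEAE rate or power statement.

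**Step 1. Trace each class of TEAE through SAP 12.**

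| Class of TEAE | Route to CEC, CAP-1002 | Route to CEC, usual care |
|---|---|---|
| Clinical endpoint | yes | yes |
| Serious | yes | yes |
| Within 24 h of infusion or reference time | yes | yes |
| After 24 h, non-serious, non-endpoint, judged related | yes | in practice does not arise |
| After 24 h, non-serious, non-endpoint, judged unrelated | no | no |

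The fourth row is an inference. Usual care receives neither product nor infusion, and the safety population is analysed by treatment received (SAP 6), but Protocol 7.13.4 exempts no arm from relatedness rating. SAP 9.2 also treats a missing relationship as related only in CAP-1002. If that imputation triggers referral, the imbalance widens.

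**Step 2. As-reported reading: unreferred TEAEs enter as reported.** In the fourth class the CEC can then alter only CAP-1002 counts. Assumptions, none from the documents: true incidence 50% in both arms, one event per affected subject, a share r of CAP-1002 events referred, and a share m of those deleted.

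Understatement of CAP-1002 incidence = 0.50 × r × m.

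- r = 5%, m = 10%: 0.50 × 0.05 × 0.10 = 0.0025; × 12 = 0.03 subjects.
- r = 25%, m = 30%: 0.50 × 0.25 × 0.30 = 0.0375; × 12 = 0.45 subjects.
- If as many as 75% were referred, m = 30%: 0.50 × 0.75 × 0.30 = 0.1125; × 12 = 1.35 subjects.

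With two independent events per affected subject, both must be deleted: at r = 25%, m = 30% this is 0.50 × 0.075² = 0.0028, or 0.3 points. Event numbers fall by r × m: 0.5% to 7.5% for r of 5-25%.

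Exact enumeration of the two-sided Fisher test at 0.05, 12 v 12, usual care at 50%:

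| CAP-1002 tabulated incidence | Rejects in favour of CAP-1002 |
|---|---|
| 50% (no bias) | 1.14% |
| 49.75% | 1.18% |
| 46.25% | 1.81% |
| 38.75% | 4.11% |

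Total two-sided rejection is 2.28% with no bias and 4.33% at 38.75%. SAP 7.3 uses Fisher's test only when a cell is below 5. With all cells at least 5, the most extreme table is 7/12 v 5/12, where chi-square = 24 × (49 − 25)² / 12⁴ = 0.67, far from significance, so using Fisher's test throughout does not change these results.

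**Step 3. Adjudicated-only reading: only adjudicated TEAEs are tabulated.** Usual care is then 0/12 for this class by construction, and late events judged unrelated vanish from both arms. Fisher p = 2 × C(12,k) / C(24,k) for k/12 v 0/12:

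- k = 4: 2 × 495 / 10,626 = 0.093
- k = 5: 2 × 792 / 42,504 = 0.037

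With 50% true incidence in both arms, and before any CEC deletion, the chance of a spurious significant CAP-1002 excess is 0.02% if 10% of affected CAP-1002 subjects have an event judged related, 1.1% at 25% and 15.8% at 50%. The displayed counts are distorted even when the test is not: at 25%, the table would show on average 12 × 0.50 × 0.25 = 1.5 v 0, when the truth is 6 v 6.

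**Step 4. The 24-hour wording.** SAP 9.2 describes its listing as "TEAEs within 24 hours of IP administration (adjudicated if judged to be related to IP or IP administration procedure"), and table 14.3.1.4 also names only IP administration. SAP 12 refers all 24-hour AEs and includes the usual-care reference time. Protocol 7.13.4 treats every AE within 24 hours of intervention as at least possibly related to the procedure, so for CAP-1002 the two wordings should select the same events. The mismatch falls on usual care.

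**The case against.** The strongest reply is that the SAP nearly answers the question itself. It says a subset is adjudicated in addition, asks for TEAEs overall as well as by relationship, and calls several listings adjudicated only as applicable. Protocol 9.5.2 requires TEAE incidence by SOC and PT, and SAP 15 declares no departure from it. All this points to the as-reported reading. I agree that it is the more natural one, but no sentence states it for the tables, and the arms still differ under it.

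Next, much is already protected. Serious, endpoint and first-24-hour events have a CEC route in both arms, the CEC is independent of the sites and manufacturer, and with at most 30 subjects the two planned listings let every change be traced. That stands and limits the weight of the point. Listings do not, however, give a between-arm incidence on a common rule.

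Also, every rate above is assumed, and the calculation covers deletion only. Renaming can raise or lower a PT count, and merging affects event numbers more than subject incidence. That stands too.

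A reader might infer that Protocol 10.1 gives the CEC a wider remit, because it mentions each randomized subject. The documents do not support this. That phrase is in the sentence on how often the committee meets. The scope sentence covers endpoint events, serious, protocol-defined and intervention-related AEs, and causes of death, which largely matches SAP 12 and opens no route for late, unrelated, non-serious events.

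**Conclusion.** The point holds in a modest form. For late, non-serious, non-endpoint TEAEs, the plan builds its two columns by different rules, and the rule for unreferred events is unstated. This rests on one inference, that relatedness to product or procedure will in practice be found only in CAP-1002.

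It is tempting to conclude that the plan flatters CAP-1002. The documents do not fix a direction. On the as-reported reading, deletion or merging lowers CAP-1002 counts; on the adjudicated-only reading, usual care is set to zero and CAP-1002 looks worse. Renaming can move a PT count either way.

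The size cannot be derived from the documents. On the as-reported reading, with 5-25% referred and 10-30% of those deleted, the effect is under half a subject in 12, and the chance of a significant result favouring CAP-1002 rises from 1.1% to at most 1.8%. Even at 75% referred and 30% deleted, total rejection stays below the nominal 5%. The practical concern is therefore the displayed counts and the open rule, more than the p-values. The 24-hour mismatch is a separate, minor wording matter.

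**What to change.** 1. Add to SAP Appendix B as-reported, MedDRA-coded TEAE incidence and number tables with between-arm comparison, built by the same rule in both arms. Read any overall, SOC or PT difference from these and the adjudicated tables together; neither replaces the other.
2. State in SAP 9.2 that TEAEs not referred to the CEC enter the adjudicated tables as reported. This rules out the adjudicated-only reading.
3. As a minor alignment, extend the 24-hour listing, summary and table 14.3.1.4 to the usual-care reference window, and reconcile the related-only condition in 9.2 with SAP 12, which refers all 24-hour AEs.

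The cost is some wording changes and one extra table set from events already coded and listed. The as-reported tables rest on unblinded investigators in an open-label trial, so they carry a reporting bias of their own. That is why they belong beside the adjudicated tables and not in their place.
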